
Section 1.3.3: Repeat Dose (Treatment Period 3)
 
Section 4.1: Overall Design
	
Section 1.3.3 (update in bold):
 
Footnote #6: “Dosing on Days 6 and 13 can be either at home or at the site” was added; and “home” was removed from “home-dosing”
 
Patient diary card dispense was added to Day 14.
 
Footnote #7 was expended by adding patient diary card dispense on Day 14 as follows “and dispense Day 14 (for evening entry) and Day 15 (morning entry) patient diary card before discharge on Day 14. The last diary card (dispensed on Day14) will be reviewed by the site via the phone call on Day 15, and returned to the site within 2 weeks from Day 15”
 
Section 4.1 (update in bold):
 
“after home dosing that day” was removed from the sentence “Participants will then return to the unit on Day 6 after home dosing that day to receive a dose in the unit on Day 7 before being discharged on Day 7 to continue home dosing from Days 8 to 12”.
	
The edits were made to: 1) provide options for participants to receive a dose either at home or at the unit upon arrival on Day 6 and Day 13; and 2) add one more patient diary card dispense on Day 14.

Section # and Name	Description of Change	Brief Rationale
Section 2.2: Background	
The last sentence of last paragraph (study 213499) has been updated as follows (update in bold):
 
“At the time of publishing this protocol amendment, 13 participants have been dosed. No SAEs or notable AEs have been observed so far”.
	This edit was made to update an ongoing study referred in the protocol.
Section 2.3.1: Risk Assessment	
Respiratory tract irritancy mitigation strategy (update in bold):
 
Safety margins were modified to “maximum observed clinical exposure following 14-day repeat doses of 1500 mcg is expected to be below the rat mean gender-averaged NOAEL systemic exposure margins (AUC: 6-14 fold; Cmax: 26-64 fold; lung deposition cover at the rat NOAEL for lung pathology: 10 fold)”
	These edits were made to update safety margins based on the new top dose of 1500 mcg.


Section 4.1: Overall Design
 
Section 4.2: Justification for Dose
	
Section 4.1 (update in bold):
 
Single Dose Treatments - “half of” was added to the second last paragraph as follows “The planned doses may be modified based on emerging safety and tolerability data but will not exceed half of the maximum single and repeat dose level administered in the FTIH Study of 3000 mcg once daily”.
 
Repeat Dose Treatment – “half of” was added to the third paragraph as follows “This planned dose may be modified based on emerging data but will not exceed half of 3000 mcg, the maximum repeat dose level administered in the FTIH Study”.
 
Section 4.2.1: Starting Dose and Dose Escalation (update in bold):
 
The sentence “This dose was also the highest dose administered and was well tolerated in the FTIH Study” was edited to “This dose was half of the highest dose (3000 mcg) administered that was well tolerated in the FTIH Study”.
 
Section 4.2.2: Safety Margins:
 
Safety margins for 1500 mcg have been updated in
	
These edits were made to justify 1500 mcg selection.

---	--	---

	
the following paragraph (update in bold).
 
“Based on the PK data generated from FTIH Study 213497, the systemic exposure of participants following 1500 mcg GSK3923868 once daily for 14 days using the CCI [REDACTED] device would be within the systemic exposure safety margins provided by the Rat IV study NOAEL (providing 26 to 64 fold cover for Cmax and 6 to 14 fold cover for AUC(0-24) based on the individual participant exposures on Day 14 with 3000 mcg once daily in the FTIH Study”.
 
Section 4.2.3: Predicted Target Engagement at Steady State:
 
Target engagement at 1500 mcg has been updated in the following paragraph and “In addition” was removed (update in bold).
 
“Modelling and simulation was conducted utilising the PBPK model and the PKPD model (incorporated the PI4KB enzyme kinetics data which accounted for competitive binding with ATP) prediction shows at steady state trough in lungs, the median TE of GSK3923868 following a
	
--	--	--

Section # and Name	Description of Change	Brief Rationale
	
1500 mcg once daily dose was CCI [REDACTED] [REDACTED] [REDACTED] as illustrated in Figure 1 below".
 
The following sentence was deleted.
 
"Additionally, for a 1000 mcg dose given using the CCI [REDACTED] device (with the assumption of dose proportionality in PK), the model predicted about CCI [REDACTED] [REDACTED] [REDACTED] [REDACTED]
 
Original Figure 1 was replaced with 1500 mcg target engagement prediction and the figure title was updated as follows (update in bold).
 
"Predicted Distribution of Percent Target Engagement (TE) at Steady State Trough (1500 mcg OD)"
	
Section 6.1: Study Intervention(s) Administered	
Table 3/Repeat Dose (Period 3):
 
Unit dose strength was changed from CCI [REDACTED] [REDACTED].
 
Dose level was changed from CCI [REDACTED] [REDACTED]
	
These edits were made to clarify that CCI [REDACTED] CCI [REDACTED] will be used for treatment period 3.

Section # and Name	Description of Change	Brief Rationale
Section 6.2: Preparation, Handling, Storage and Accountability	The bullet “ CCI XXXXXXXXXX should be kept in their primary packaging until dispensing into participant dosing bottles” was removed.	This edit was made to update the change in dispensing study intervention strategy, i.e., no sub-dispensing will be conducted.
Section 6.5.1.2: Study specific dose escalation stopping criteria	
“severe non-serious” and “and at least possibly related to the study drug” was added to the bullet
 
“Two participants experience any severe non-serious adverse event considered clinically important by the Investigator and at least possibly related to the study drug”
	This edit was made to further clarify this stopping criterium.
Section 8.2.4.2: Peak Expiratory Flow	“ and recorded in the eCRF ” was removed from “PEF will be performed at time points outlined in the SoA and recorded in the eCRF”	This edit was made to clarify that PEF data will be collected for participants to monitor their lung functions only.
Section 9: Statistical Considerations	“ and in the OPS, respectively ” was added to the end of the second paragraph.	This edit was made to clarify study reporting details.
Section 9.4.2.2: Laboratory values, vital signs, 12-lead electrocardiogram and Spirometry	“ FVC ” was removed from the last bullet.	FVC data will be collected at screening only and not for analyses.

Section # and Name	Description of Change	Brief Rationale

1. PROTOCOL SUMMARY

1.1. Synopsis

Protocol Title: A randomized, double-blind, placebo controlled, single and repeat dose study to assess the safety, tolerability and pharmacokinetics of inhaled GSK3923868 in participants with Chronic Obstructive Pulmonary Disease (COPD)

Brief Title: A study to investigate safety, tolerability, and PK of GSK3923868 inhalation powder in COPD

Rationale:

GSK3923868 is a selective and potent inhibitor of phosphatidylinositol 4-kinase beta (PI4KB) being developed for respiratory disease and specifically the treatment of rhinovirus associated exacerbations of chronic obstructive pulmonary disease (COPD) and asthma.

Data from this Phase 1 study will provide an assessment of the safety, tolerability, and pharmacokinetics of GSK3923868 inhalation powder in participants with stable COPD to support future studies in which COPD patients will be treated at the onset of cold-like symptoms and possibly at the beginning of an infective exacerbation. GSK3923868 is not an immunomodulatory drug.

Objectives and Endpoints:

Objectives	Endpoints
Primary	

 To assess the safety and tolerability of GSK3923868 following single and repeat inhaled administration in participants with COPD 	
 Occurrence of adverse events (AEs) and serious adverse events (SAEs). Clinically significant changes in laboratory values, vital signs, 12-lead electrocardiogram (ECG) and spirometry measurements up to Follow Up.

Objectives	Endpoints

Secondary
 
 • To evaluate the plasma pharmacokinetics of GSK3923868 following single and repeat inhaled administration in participants with COPD 	
Derived pharmacokinetic parameters as data permit, including (but not limited to):
 
 • Area under the plasma-concentration time curve (AUC): area under the concentration-time curve from time 0 (predose) to 24 hours post dose administration following the first dose (AUC[0-24]) or area under the concentration-time curve from time 0 to the time of the last quantifiable concentration (AUC[0-t]) for single dose and area under the concentration-time curve from time 0 (predose) to 6 hours post dose administration following the first dose (AUC[0-6]) for repeat dose • Maximum observed plasma drug concentration (Cmax), time to maximum observed plasma drug concentration (Tmax)

Overall Design:

This is a single cohort, randomized, double-blind, placebo controlled single and repeat dose study designed to assess the safety, tolerability and plasma PK of GSK3923868 administered as an inhalation powder blend (GSK3923868 **CCI** ██████████) using the **CCI** ██████████ inhaler in participants with stable COPD. This study contains two parts, a single ascending dose followed by 14-days repeat dosing.

The single ascending dose part will assess two dose levels of GSK3923868 inhalation powder or placebo across two treatment periods in a single crossover cohort of participants.

The repeat dose part will assess one dose level of GSK3923868 inhalation powder or placebo in one treatment period in the same cohort of participants.

Brief Summary:

The purpose of this study is to measure safety, tolerability and pharmacokinetics of single or repeat inhaled doses of GSK3923868 in participants with stable COPD. The study treatment will be one day for the single dose assessments and 14 days for the repeat dose assessment. The study duration will be from 64 to 71 days. The visit frequency is detailed in the Schedule of Activities (SoA) in Section 1.3

Number of Participants:

A total of approximately 12 participants with COPD will be enrolled in this study. Sufficient patients will be screened and those who meet the study entry criteria will be randomized to receive GSK3923868 inhalation powder or placebo in a 3:1 ratio with the intention of a minimum of 8 and a maximum of 12 participants to complete the study.

Note: Enrolled means a participant agrees to participate in a clinical study following completion of the informed consent process and screening. Potential participants who are screened for the purpose of determining eligibility for the study, but do not participate in the study, are not considered enrolled, unless otherwise specified by the protocol. A participant will be considered enrolled if the informed consent is not withdrawn prior to participating in any study activity after screening.

Intervention Groups and Duration:

This single cohort, randomized, double-blind, placebo-controlled study contains two single and one repeat dose treatments.

Single Dose

The single dose treatments will assess two ascending single doses of GSK3923868 as an inhalation powder using the **cci** inhaler in one cross-over cohort of participants with COPD. Participants will receive single ascending doses of GSK3923868 inhalation powder or matching placebo (3:1 ratio) in two treatment periods. The proposed starting dose is 500 mcg. Progression to the next single dose level of 1000 mcg will occur on an individual participant basis and only if, in the judgement of the Investigator, it is supported by the safety and tolerability profile in that patient taking 500 mcg.

Participants will be enrolled for approximately 42 days for the single dose assessments (up to 30 days screening, 2 assessment/washout periods up to 6 days each).

Repeat Dose

The repeat dose treatment will assess 1500 mcg of GSK3923868 in the same cohort of participants that has completed single dose assessments. Participants will receive either GSK3923868 or placebo as an inhalation powder via **cci** inhaler (3:1 ratio) once daily for 14 days. Progression to repeat dosing will occur on an individual participant basis and only if the Investigator agrees it is supported by the safety and tolerability profile of single doses.

Participants will be enrolled for approximately 15 days for the repeat dose period and follow-up period from 7 to 14 days.

[figure not shown]
In total, participants will be enrolled for approximately 64 to 71 days in the study (42 days for two single dose periods including screen and washouts, and 15 days for one repeat dose period including a 7 to 14-day follow-up).

Data Monitoring/ Other Committee: No

Regular (i.e., every 4 weeks) meetings between the Investigator and Sponsor study teams will review all available safety data across all participants in the study.

1.2. Schema

Cohort 1 (n=12)

1.3. Schedule of Activities (SoA)

1.3.1. Screen and Follow Up

Procedure	Screening ¹ (up to -30 days before Day 1)	Early Discontinuation/Withdrawal Visit (7 ± 2 days post last dose)	Follow Up Phone Call (7 to 14 days post last dose)
Phone Call			X
Informed Consent	X		
Review Inclusion and Exclusion Criteria	X		
Demography	X		
Medical & Disease History	X		
Full Physical Examination (includes height, weight and BMI)	X		
Brief Physical Examination		X	
Alcohol Urine Test	X	X	
Urine Drug Screen	X	X	
COVID-19 Screening ²	X	X	
AE Review		X	X
SAE Review	X	X	X
Concomitant Medication Review	X	X	X
Inhaler Training	X		
Spirometry (FEV1 & FVC) ³	X	X	
Vital Signs ⁴	X	X	
12-Lead Safety ECG ⁵	X	X	
Safety Laboratory Assessment ⁶	X	X	
Urinalysis	X	X	
Serum FSH and Estradiol ⁷	X		
Urine Pregnancy Test	X	X	
HIV, Hepatitis B and C Screening	X		

Procedure	Screening ¹ (up to -30 days before Day 1)	Early Discontinuation/Withdrawal Visit (7 ± 2 days post last dose)	Follow Up Phone Call (7 to 14 days post last dose)
PK Blood Sample		X	

1. Screening may be performed across multiple visits if necessary.
2. To be performed according to local site policy.
3. Pre- and post-bronchodilator FEV1, predicted FEV1 and FVC are needed at screen only.
4. Includes systolic and diastolic blood pressure, heart rate, respiration rate and tympanic temperature
5. Triplicate ECGs will be obtained at screening and single ECGs at all other occasions.
6. Clinical chemistry, hematology.
7. As needed in women of nonchildbearing potential only

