1.3.2. Single Ascending Dose (Treatment Periods 1 and 2)

Procedure	D-1	Treatment Periods 1 and 2										D2	D3
		Pre-dose	0h	5m	15m	30m	45m	1h	2h	4h	6h		
Site Visit	X							X					
Site Overnight Stay ¹	X							X					
Discharge from Site												X	
Phone Call													X
Review Inclusion and Exclusion Criteria	X												
Alcohol Urine Test	X												
Urine Drug Screen	X												
COVID-19 Testing ²	X												
Brief Physical Examination	X												
Inhaler Training (refresher) ³	X												
Randomisation (Period 1 only)		X											
Treatment Administration ⁴			X										
AE Review (include washout)				←								→	
SAE Review (include washout)			←									→	
Conmed Review			←									→	
Spirometry (FEV1)		X						X				X	
Vital Signs ⁵		X					X					X	X
12-Lead Safety ECG (single)		X						X				X	
Laboratory Safety Assessment ⁶	X											X	
Urinalysis	X												
Urine Pregnancy Test	X												
PK Blood Sample		X		X	X	X	X	X	X	X	X		
Genetic sample ⁷ (optional)		X											

1. Day -1 site admission would be optional.
2. To be performed according to local site policy on Day -1.
3. To be provided before first dose administration. If necessary, another inhaler refresher training may be provided in treatment period
4. Participants should fast for at least 6 hours before dosing until 1 hour post-dose. No water from 1 hour before dosing until 1 hour post-dose. See Section 5.3 for details.
5. Includes systolic and diastolic blood pressure, heart rate, respiration rate and tympanic temperature. Tympanic temperature will be measured once per day in the morning only.
6. Clinical chemistry and hematology only.
7. Genetic sampling can be conducted at any onsite visit during the study.

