7.1.2. QTc Stopping Criteria

The Fridericia QT correction (QTcF) formula will be used in the study.

A participant that meets either bulleted criteria based on the average of triplicate ECG readings will be considered for withdrawal from the study intervention:

- $QTcF > 500$ msec
- Change from baseline: $QTcF > 60$ msec

Baseline QTcF will be based on the pre-dose ECGs collected before the first dose.

If a clinically significant finding is identified after enrolment, the investigator or qualified designee will determine if the participant can continue in the study and if any change in participant management is needed. This review of the ECG printed at the time of collection must be documented. Any new clinically relevant finding should be reported as an AE.

Note: Single safety ECG assessments are performed following enrolment in this study. If a single ECG should meet the criteria above, obtain two further ECGs over a brief period (e.g., 5 to 10 minutes). The averaged QTcF value of the 3 ECGs should be used to determine whether the participant should be withdrawn from the study.

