9.4.1. General Considerations

Unless otherwise specified, baseline will be the last value/assessment before the first dose of study treatment (Day 1 pre-dose). If there are multiple assessments collected at the same scheduled time, the average of these assessments will be used as the baseline.

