6.2.5. Multiple measurements at One Analysis Time Point

When triplicate ECG assessments are taken, mean of the measurement will be calculated first and summary statistics will be based on the calculated mean. This will apply to both baseline and post baseline assessments.

For lab tests on a study day, if more than one assessment is taken on the same day, the test from a central lab will be taken over the test from a local lab. If multiple assessments are taken from the same type of lab, the worst case will be used.

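### The QTcF baseline is one pre-dose tracing, while the stopping rule averages three on the post-dose side only; a triplicate Period 1 Day 1 baseline would be a cheap gain in precision and would settle a wording conflict

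*Protocol*

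**What the plan says.** Footnote 5 to the screening and follow-up schedule (Protocol 1.3.1) states: "Triplicate ECGs will be obtained at screening and single ECGs at all other occasions". In the schedule for Periods 1 and 2 (Protocol 1.3.2) the row that contains the Day 1 pre-dose ECG begins "12-Lead Safety ECG (single". The Period 3 schedule (1.3.3) labels its ECG row the same way.

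Under Protocol 9.4.1, unless otherwise specified, "baseline will be the last value/assessment before the first dose of study treatment (Day 1 pre-dose"; SAP 4.1.2 agrees. Section 7.1.2 adds for the stopping rule: "Baseline QTcF will be based on the pre-dose ECGs collected before the first dose". Section 8.2.3 repeats this, also in the plural.

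On how the rule is judged, 7.1.2 states: "A participant that meets either bulleted criteria based on the average of triplicate ECG readings will be considered for withdrawal from the study intervention". One of the two criteria is a QTcF change from baseline above 60 msec. A note in the same section recognises that ECGs after enrolment are single and provides: "If a single ECG should meet the criteria above, obtain two further ECGs over a brief period (e.g., 5 to 10 minutes". The three values are then averaged.

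SAP 6.2.5 averages triplicate ECGs when they are taken and adds: "This will apply to both baseline and post baseline assessments". SAP 6.2.1 lists a QTc increase from baseline above 60 msec as a value of potential clinical importance. SAP 4.2.1 makes such values part of the primary endpoint.

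**The concern.** Three descriptions of the baseline do not fit together. The schedule provides one pre-dose tracing. Sections 7.1.2 and 8.2.3 read as though there were several. The SAP has a rule for averaging baseline triplicates that the schedule never supplies. The only scheduled triplicate is at screening, up to 30 days earlier, and it is not the baseline.

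The confirmation step does not close this gap, because it replicates only the post-dose value. A baseline tracing that happens to read e msec too high lowers every later QTcF change for that participant by e, and no number of further post-dose tracings removes it. As far as the schedule tables can be read, a completer has 11 later scheduled ECGs: two in Period 1, three in Period 2 and six in Period 3.

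The affected quantities are the >60 msec criterion for the individual participant, the temporary halt when two participants meet the QTc criteria (Protocol 6.5.1.2), the flag in the primary endpoint, and the summaries of change from baseline. A baseline that was not replicated before the first dose cannot be replicated afterwards.

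**Working it through.** The plan gives no figure for ECG variability or for the precision of QTcF change, so there is nothing to reproduce. The inputs are:

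- From the documents: one baseline tracing (nb = 1); one post-dose tracing, extended to three if the first exceeds the threshold; threshold 60 msec.
- Assumed: s, the SD between tracings on one occasion, 6 to 12 msec; d, the day-to-day SD of a participant's QTcF, 0 or 8 msec. Replicates on one occasion reduce s but not d.

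**SD of a change using one post-dose tracing:** sqrt(2d² + s² + s²/nb). With s = 10:

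- d = 0: sqrt(100 + 100) = 14.1 with a single baseline and sqrt(100 + 33.3) = 11.5 with a triplicate, a reduction of 18%.
- d = 8: sqrt(128 + 200) = 18.1 and sqrt(128 + 133.3) = 16.2, a reduction of 11%.

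**Share of the variance of a confirmed change (mean of three post-dose) due to the one baseline tracing:** s²/(2d² + s² + s²/3). With s = 10 this is 100/133.3 = 75% at d = 0 and 100/261.3 = 38% at d = 8.

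**The 7.1.2 procedure.** A case is confirmed if the first post-dose reading minus baseline exceeds 60 and the mean of three post-dose readings minus the same baseline also exceeds 60. Errors are taken as normal, with 2,000,000 simulated cases per setting. Each cell gives single versus triplicate baseline.

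| s | d | True rise 50, confirmed as >60 | True rise 70, missed |
|---|---|---|---|
| 6 | 0 | 5% vs 1% | 14% vs 8% |
| 10 | 0 | 14% vs 7% | 29% vs 23% |
| 12 | 0 | 18% vs 10% | 34% vs 28% |
| 6 | 8 | 19% vs 17% | 28% vs 26% |
| 10 | 8 | 22% vs 18% | 34% vs 32% |
| 12 | 8 | 23% vs 19% | 37% vs 35% |

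As a check, consider the mean of three alone, without the trigger, at s = 10, d = 0 and a true rise of 50. The chance of exceeding 60 is 1 − Φ(10/11.55) = 19% with a single baseline and 1 − Φ(10/8.16) = 11% with a triplicate. Requiring the trigger as well lowers these to the 14% and 7% in the table.

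**No true change.** With a single baseline and s = 10, the chance that the mean of three exceeds 60 is 1 − Φ(60/11.55), about 1 in 10 million, at d = 0. At d = 8 it is 1 − Φ(60/16.17), about 1 in 10,000. Requiring the trigger makes both smaller.

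**The case against.** The best defence is that the protocol chose single ECGs knowingly. The note in 7.1.2 says they are single after enrolment and builds in confirmation. Both SAP rules are conditional: 4.1.2 averages if there are multiple assessments, and 6.2.5 averages when triplicates are taken. They work unchanged with a single baseline. This stands. A reader might infer that the SAP assumes an averaged baseline and is therefore wrong, but its text does not support that.

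The gain is also smaller than replicate error alone suggests. Day-to-day variation cannot be averaged out on one occasion, and with an assumed SD of 8 msec it removes much of the benefit. This stands too, and it is why both settings are shown.

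The practical risk is limited. The protocol's risk table lists no QT risk, doses up to 3000 mcg are reported as well tolerated in healthy participants, and the >500 msec criterion uses no baseline. A reader might infer that noise could stop participants who have no QTcF change, but the last calculation shows that this is negligible.

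A reader might also infer that the comparison of 9 active with 3 placebo participants within a period is seriously weakened. No such test is planned. Nine of the twelve participants receive both active and placebo, and with one study baseline its error cancels in their within-participant contrasts.

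None of this explains the plural in 7.1.2 and 8.2.3, or why only the post-dose side is replicated.

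**Conclusion.** The point holds as a cheap improvement in precision together with a wording conflict that must be reconciled. Under the schedule the QTcF baseline is a single tracing, and the confirmation step leaves its error untouched. The effect matters for true changes near 60 msec, in both directions, and for the individual change profiles.

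At a replicate SD of 10 msec, a triplicate baseline cuts wrong confirmation of a true 50 msec rise by 4 to 7 percentage points and missed detection of a true 70 msec rise by 2 to 6 points. The smaller figure in each range assumes a day-to-day SD of 8 msec and the larger assumes none. All SDs are assumptions. The finding that the baseline is unreplicated does not depend on them, but its size does. It does not threaten the study's conclusions.

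**What to change.** Change footnote 5 of Protocol 1.3.1 and the ECG row of 1.3.2 so that the Period 1 Day 1 pre-dose ECG is taken in triplicate and averaged. Because 1.3.2 covers both single-dose periods, mark the triplicate as Period 1 only. Then align 7.1.2, 8.2.3 and 9.4.1 of the protocol and 4.1.2 of the SAP so that all name this one baseline. SAP 6.2.5 already handles the averaging. No threshold or stopping rule needs to change.

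The cost is two extra tracings, once per participant, within the recording period of up to 10 minutes that 8.2.3 already describes for triplicates. It helps only participants not yet dosed. If the sponsor keeps a single baseline, the same sections should say so and drop the plural; that removes the conflict but not the imprecision.

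Averaging in the screening triplicate is not a sound substitute. That reading may be up to 30 days old. It was also selected by the exclusion of QTcF above 450 msec, which tends to bias the baseline low and the measured change high.
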